## 1.0 BACKGROUND AND RATIONALE

### 1.1 Acute GVHD

Hematopoietic cellular transplantation (HCT or BMT) is an important treatment for high-risk hematologic malignancies whose curative potential depends on the graft-versus-leukemia (GVL) effect. Graft-versus-host disease (GVHD), the major cause of non-relapse mortality (NRM) after HCT, is closely associated with GVL. Pre-transplant clinical risk factors for GVHD include the degree of human leukocyte antigen (HLA) match between donor and recipient, recipient age, donor type, and conditioning regimen intensity. Some centers use one or more of these risk factors to guide GVHD prophylaxis, such as the use of anti-thymocyte globulin when the donor is not an HLA-identical sibling, but such approaches are globally immunosuppressive and carry their own risks, in particular of opportunistic infections.

[figure not shown]
Acute GVHD affects 40% to 60% of patients and targets the skin, liver, and gastrointestinal (GI) tract. The median onset of acute GVHD is approximately 1 month after transplant. The initial treatment for GVHD is typically high doses of systemic corticosteroids, but up to 50% of patients do not respond to this approach. Steroid refractory (SR) GVHD, which most often involves the GI tract, is the primary driver of lethal GVHD, and by extension, non-relapse mortality after HCT. However, until now there has been no reliable method to identify the patients at high risk for SR GVHD before GVHD develops.

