The preliminary data for this study was generated from patients transplanted at multiple centers with heterogeneous GVHD treatment practices. In order to develop “real world” experience in this study, institutional GVHD treatment practices are permitted unless their use is explicitly prohibited.  
  
Patients who develop GVHD will be treated as per institutional standards with systemic and non-systemic treatments such as topical steroids or non-absorbable steroids for GI GVHD. If systemic steroid treatment is initiated the recommended starting dose is **prednisone 2 mg/kg/day**. Centers may use a starting dose of 2 mg/kg of methylprednisolone if that is their institutional practice. Additional agents for the purpose of treating GVHD (e.g., etanercept, extracorporeal photopheresis, ATG) are not allowed. The initiation of systemic GVHD treatment beyond continuation or adjustment of GVHD prophylaxis medications (see section 5.1.6) and corticosteroids will be considered the initiation of second line GVHD treatment and considered a treatment failure. **Study treatment with alpha-1-antitrypsin continues during GVHD treatment until all 16 doses have been administered or ten weeks have elapsed from the start of AAT, whichever comes first.**

GVHD treatment will be tapered according to local institutional tapering practices. A recommended taper is provided in the appendices.

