### 5.3 Concomitant Medications/Treatments

Concomitant use of other investigational agents is not permitted during the treatment phase of the study without PI approval.

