### 5.5 Duration of Therapy

The duration of protocol therapy on this study is eight weeks (16 doses). Protocol therapy will end after the 16th dose of alpha-1-antitrypsin has been administered or if any of the following criteria apply:

- Patient voluntarily withdraws from treatment **OR**
- General or specific changes in the patient's condition render the patient unacceptable for further treatment in the judgment of the investigator **OR**
- Ten weeks has elapsed since the first dose of AAT

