### **5.8 Off Study Criteria**

**Patients can be taken off study at any time at their own request, or they may be withdrawn at the discretion of the investigator for safety, behavioral or administrative reasons. The reason(s) for discontinuation from study will be documented and may include:**

- 5.8.1 Patient withdraws consent (termination of treatment and follow-up);
- 5.8.2 Loss of ability to freely provide consent through imprisonment or involuntary incarceration for treatment;
- 5.8.3 Patient is unable to comply with protocol requirements;
- 5.8.4 The subject has any disorder or condition that in the investigator's judgment may impede the participant's participation in the study, pose increased risk to the participant, or confound the results of the study
- 5.8.5 Patient becomes pregnant (pregnancy to be reported along same timelines as a serious adverse event);
- 5.8.6 Termination of the study;
- 5.8.7 Patient completes protocol treatment and follow-up criteria.

The informed consent documents will emphasize the importance of collecting outcome data from individuals who choose to discontinue treatment during the study, and participants will be encouraged to provide this information whether or not they complete the anticipated course of study treatment.

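### Section 5.1.7 bans additional GVHD agents without an exception for steroid failure, and 11.3 drops the day-28 limit on added therapy that 2.3, 7.1.3 and 11.1 apply to the primary endpoint

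*Combined protocol and SAP*

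**What the plan says.** **Treatment rule.** Section 5.1.7 sets a general principle: "institutional GVHD treatment practices are permitted unless their use is explicitly prohibited". It recommends a steroid starting dose and then says: "Additional agents for the purpose of treating GVHD (e.g., etanercept, extracorporeal photopheresis, ATG) are not allowed". The sentence after that deals with systemic GVHD treatment beyond prophylaxis drugs and corticosteroids. Starting such treatment "will be considered the initiation of second line GVHD treatment and considered a treatment failure". AAT continues while GVHD is being treated.

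**Second-line therapy elsewhere.** Section 7.1.5 makes steroids the first line and any added systemic immunosuppression the second. Section 11.1 lists the number of lines of GVHD therapy as a secondary endpoint.

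**Primary endpoint.** Sections 2.3, 7.1.3 and 11.1 call GVHD steroid-refractory in two cases: there is no CR or PR at day 28 of systemic steroids, or further immunosuppression is given before day 28. Section 11.3, the analysis text, lists three failure routes for the same endpoint: death, no response to steroids by day 28, and the start of additional systemic immunosuppression for GVHD. In that list the day-28 condition belongs to the second route only.

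**Decision rule.** Section 11.2 calls the approach promising if 6 or fewer of 30 patients develop steroid-refractory GVHD, against a historical rate of 28% and a target of 15%.

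**The concern.** There are two separate wording problems.

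The first concerns patient care. Section 1.1 says that steroid-refractory GVHD "is the primary driver of lethal GVHD, and by extension, non-relapse mortality after HCT". A site that follows 5.1.7 to the letter cannot give a second agent to such a patient without deviating from the protocol. Yet other sections plan to record that second agent as a line of therapy.

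The second concerns the primary endpoint. If 11.3 and the three definition sections disagree about late added therapy, the same patient can be an event or a non-event depending on which section the analyst follows. The decision is a bare count against a cutoff of 6, so a single patient can matter.

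**Working it through.** **1. The plan's own figures.** Inputs from 11.2: n = 30, go if X ≤ 6, rates 28% and 15%, one-sided exact test, target alpha 0.23, power 85%.

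- P(X ≤ 6 | 30, 0.28) = 0.2238, below the 0.23 target.
- P(X ≤ 6 | 30, 0.15) = 0.8474, which agrees with 85%.
- P(X ≤ 7 | 30, 0.28) = 0.3676, so 6 is the correct cutoff.

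The design reproduces. Neither wording point touches these figures.

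**2. Does anything lift the ban in 5.1.7?**

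- The institutional-practice principle yields to explicit prohibitions, and the ban is one.
- The following sentence ("will be considered the initiation of second line GVHD treatment and considered a treatment failure") classifies added therapy. It does not permit it.
- 5.1.8 covers supportive care, and 5.4 covers other conditions and transplant complications.
- 5.3 covers investigational agents only. It also shows that the protocol can write an exception into a ban: "Concomitant use of other investigational agents is not permitted during the treatment phase of the study without PI approval".
- 5.5 ends AAT when changes in the patient's condition "render the patient unacceptable for further treatment in the judgment of the investigator". Under 5.8, "they may be withdrawn at the discretion of the investigator for safety, behavioral or administrative reasons". Both stop something; neither authorises a second agent.

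No passage supplies the exception.

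**3. Timing of added therapy, side by side.**

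| Section | Added systemic GVHD therapy counts as | Day-28 limit |
|---|---|---|
| 2.3, 7.1.3, 11.1 | steroid-refractory GVHD | yes |
| 11.3 | primary-endpoint failure | none stated |
| 5.1.7 | treatment failure (primary endpoint not named) | none stated |
| 7.1.5 | second line, failure to respond to steroids (primary endpoint not named) | none stated |

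The direct conflict about the primary endpoint is between 11.3 and the first row.

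**4. Length of the disputed window.** If systemic steroids start on HCT day s, an agent added from day s + 28 to day 100 is scored differently. The window is 100 − (s + 28) = 72 − s days.

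- s = 14: 58 days
- s = 30: 42 days
- s = 45: 27 days
- s = 60: 12 days
- s = 72: 0 days, the date that 11.1 itself uses

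The values of s are illustrative. For s = 30 the nearest anchor is 1.1: "The median onset of acute GVHD is approximately 1 month after transplant". That is onset of GVHD, not the start of steroids.

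**5. One patient.** Take a patient in PR on steroid day 28 who starts another agent on steroid day 35, before HCT day 100. Under 2.3, 7.1.3 and 11.1 the patient is not steroid-refractory. Under 11.3 the patient fails. If 6 others have failed, the count is 6 (go) under one rule and 7 (no go) under the other.

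**6. Sensitivity, on assumption only.** The documents do not give the share of day-28 responders who later receive a new agent. If the 11.3 rule added e percentage points to the 15% target rate, P(X ≤ 6) would be:

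| e | P(X ≤ 6) |
|---|---|
| 0 | 0.847 |
| 2 | 0.761 |
| 3 | 0.712 |
| 5 | 0.607 |
| 7 | 0.499 |
| 10 | 0.348 |

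These values show how steep the rule is. They do not estimate what will happen.

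**The case against.** The best defence of 5.1.7 is context. The ban directly follows the sentences on steroid dose, the paragraph opens by deferring to institutional standards, and the next sentence says how second-line treatment is scored. On that reading the ban covers add-ons to initial steroids, and the defect is a missing qualifier. This is the likely intent. It does not remove the problem, because the qualifier is written nowhere and the sentence governs care at five centers.

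A reader might infer that the protocol means to withhold rescue therapy. The documents do not support that: 7.1.5 and the lines-of-therapy endpoint assume such therapy is given. A reader might also count every section that scores added therapy (2.3, 7.1.1, 7.1.3 and 11.3 as well) as proof that it is allowed. That goes too far, since a failure-scoring rule can equally be there to handle prohibited use. Only 7.1.5 and 11.1 clearly treat it as ordinary care.

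Nor should the expected number of steroid-refractory patients, 30 × 0.15 = 4.5 to 30 × 0.28 = 8.4, be read as patients denied rescue. It is the expected endpoint count, and by definition it includes patients who are refractory because they already received a second agent.

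On timing, one can say that 11.3 is shorthand for a definition given consistently three times. That is plausible, but 11.3 is the analysis text and lists the added-therapy route on its own. The objection does succeed for 5.1.7 and 7.1.5: neither names the primary endpoint, so their missing day-28 limit does not conflict with it.

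**Conclusion.** Both points hold, and both passages are wrong as written.

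The first is a literal bar to rescue therapy that the authors probably did not intend. Its consequence is a protocol deviation for any patient given a second agent after steroids fail.

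The second is a conflict between 11.3 and three other sections over day-28 responders who receive another agent before HCT day 100. The number of such patients is not given. A reader might infer that the primary result is biased by a known amount, and the documents do not support that. Within the trial, the 11.3 rule can only add failures on this point. The effect on the comparison also depends on how the 28% control rate was counted, which the documents do not say. All that can be claimed is that the count is not uniquely defined for these patients and that one of them could turn 6 into 7.

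The sample size of 30, alpha, power and the cutoff stand.

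**What to change.** **Section 5.1.7.** State that additional systemic agents may not be added as part of initial steroid therapy for GVHD, and that second-line therapy is permitted once the treating physician judges that steroids have failed.

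**Section 11.3.** First confirm how the 28% historical rate was counted. If it counted added therapy only before day 28 of systemic steroids, put that limit on the added-therapy route in 11.3, in line with 2.3, 7.1.3 and 11.1. If it did not, comparability with the control rate should decide the rule, and the four sections should then be made to agree on it.

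No edit to 7.1.5 is needed.

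**Cost.** One clause in 5.1.7, one phrase in 11.3 and a check of the historical definition. There are no added patients, procedures, data or tables. Sites keep the institutional flexibility that 5.1.7 intends.

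**Not resolved by this.** Section 11.3 also counts death as a failure, while 2.3, 7.1.3 and 11.1 do not. That is a separate point and needs its own decision.

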#### 5.1.8 Ancillary therapies

Ancillary/supportive care measures for acute GVHD such as the use of anti-motility agents for diarrhea, including octreotide, is allowed at the discretion of the treating physician. Use of ursodiol to prevent/reduce gall bladder sludging, or prevent hepatic transplant complications is allowed according to institutional guidelines

#### 5.1.9 Supportive Care Guidelines

All patients should receive the following:

- Transfusion support per institutional practice
- Anti-infective prophylaxis against herpes virus is required but otherwise institutional practice can be followed.
- Anti-infective prophylaxis against *Pneumocystis jiroveci*, bacterial and fungal infections according to standard institutional guidelines.
- Pre-emptive monitoring and treatment for CMV infections is required but otherwise institutional practice can be followed.

### 5.2 Toxities and Dosing Delays/Dose Modifications

Any patient who receives treatment on this protocol will be evaluable for toxicity. Each patient will be assessed for the development of toxicity according to the Time and Events Table (Section 6.4). Toxicity will be assessed according to the NCI Common Terminology Criteria for Adverse Events (CTCAE), version 4.0.

The dose of Glassia will not be modified. In the event of a SAE causally related to study drug, Glassia should be discontinued and the patient will be included in all analyses of safety and efficacy.

### 5.3 Concomitant Medications/Treatments

Concomitant use of other investigational agents is not permitted during the treatment phase of the study without PI approval.

### 5.4 Other Modalities or Procedures

Patients who have undergone allogeneic hematopoietic cell transplantation are often simultaneously being treated for other conditions and transplant-related complications. Such treatments will be considered distinct from the study drug treatment.

### 5.5 Duration of Therapy

The duration of protocol therapy on this study is eight weeks (16 doses). Protocol therapy will end after the 16th dose of alpha-1-antitrypsin has been administered or if any of the following criteria apply:

- Patient voluntarily withdraws from treatment **OR**
- General or specific changes in the patient's condition render the patient unacceptable for further treatment in the judgment of the investigator **OR**
- Ten weeks has elapsed since the first dose of AAT

### 5.6 Off Treatment Criteria

Patients will be removed from receiving the investigational drug when any of the criteria listed in Section 5.5 apply. The reason for ending investigational drug therapy and the date

the patient was removed from treatment will be documented in the study record. All patients who discontinue treatment should comply with protocol specific follow-up procedures as outlined in Section 5.7. The only exception to this requirement is when a subject withdraws consent for all study procedures.

### **5.7 Duration of Follow-Up**

Patients will be followed until 1 year post-HCT, withdrawal of consent or until death, whichever occurs first. HCT patients are followed closely and frequent clinical evaluations are the norm. The following outlines the minimum frequency of follow-up evaluations, it is anticipated that the majority of patients will be evaluated more frequently.

During the first 8 weeks of participation (i.e., through the last dose of alpha-1-antitrypsin), patients will be seen twice weekly for study drug administration. GVHD staging should be performed approximately weekly through day 100 post-HCT as part of the standard of care for HCT recipients. Patients will be evaluated at least monthly until 6 months post-HCT than again at one year post-HCT. If GVHD develops during the first six months post-HCT, staging and treatment response should be evaluated at least weekly for four weeks as part of the standard of care for patients who develop GVHD.

### **5.8 Off Study Criteria**

**Patients can be taken off study at any time at their own request, or they may be withdrawn at the discretion of the investigator for safety, behavioral or administrative reasons. The reason(s) for discontinuation from study will be documented and may include:**

- 5.8.1 Patient withdraws consent (termination of treatment and follow-up);
- 5.8.2 Loss of ability to freely provide consent through imprisonment or involuntary incarceration for treatment;
- 5.8.3 Patient is unable to comply with protocol requirements;
- 5.8.4 The subject has any disorder or condition that in the investigator's judgment may impede the participant's participation in the study, pose increased risk to the participant, or confound the results of the study
- 5.8.5 Patient becomes pregnant (pregnancy to be reported along same timelines as a serious adverse event);
- 5.8.6 Termination of the study;
- 5.8.7 Patient completes protocol treatment and follow-up criteria.

The informed consent documents will emphasize the importance of collecting outcome data from individuals who choose to discontinue treatment during the study, and participants will be encouraged to provide this information whether or not they complete the anticipated course of study treatment.

### **5.9 Patient Replacement**

Patients who enroll in the study but do not receive any study treatment will be replaced. Patients who initiate study treatment but miss more than two doses due to non-compliance will also be replaced. The number of patients and reason(s) for replacement will be recorded and will be used to assess the feasibility of the study design.

## **6.0 STUDY PROCEDURES**

### **6.1 Screening/Baseline Procedures**

Assessments performed exclusively to determine eligibility for this study will be done only after obtaining informed consent. Assessments performed for clinical indications (not exclusively to determine study eligibility) may be used for baseline values even if the studies were done before informed consent was obtained. Frequent monitoring of clinical chemistry and hematology is routine in HCT patients. This study does not require specific laboratory monitoring other than specified below.

The screening procedures include:

6.1.1 **Informed Consent** (informed consent can be obtained any time up to Day 7 post-HCT).

6.1.2 **Demographics**

6.1.3 **Review subject eligibility criteria** (Eligibility criteria must be assessed between days 4-7 post-HCT. For patients who are screened again at day 14, eligibility criteria must be re-assessed between days 11-14 post-HCT).

6.1.4 **Review concomitant medications** (immunosuppressants and GVHD prophylaxis medications only)

6.1.5 **Adverse event assessment**

Baseline adverse events will be assessed and preexisting conditions will be recorded. See Section 8.0 for Adverse Event monitoring and reporting.

6.1.6 **Serum chemistries (within 3 days prior to enrollment)**

ALT/SGPT, AST/SGOT, and total bilirubin are required for assessment of exclusion criteria within 3 days prior to enrollment.

### **6.2 Follow-Up Procedures**

The following outlines the minimum frequency of follow-up evaluations, it is anticipated that the majority of patients will be evaluated more frequently.

During the first 8 weeks of participation (i.e., through the last dose of alpha-1-antitrypsin), patients will be seen twice weekly for study drug administration. GVHD staging should be performed weekly during the first eight weeks at intervals at the visit closest to 7 day interval from Study Day 0 (i.e., Study Day 7, 14, 21, etc). Between Study Day 56 and Study Day 100, GVHD staging should be performed no less than every other week. Weekly staging is preferred and if performed should be reported on the case report forms. Patients will also be evaluated at six months and one year post-enrollment for survival, relapse, acute and chronic GVHD. If acute GVHD develops during the first 100 days post enrollment, the staging, immunosuppression medications and treatment response should be determined at least weekly for four weeks to assess the primary study endpoint.

Follow-up studies are detailed in the Time and Events Table is section 6.3.

### 6.3 Time and Events Table

	CALENDAR BASED ASSESSMENTS													GVHD DRIVEN ASSESSMENTS 		
	Screening HCT Day 7 HCT Day 14 	Study day 0	Study day 7	Study day 14	Study day 21	Study day 28	Study day 35	Study day 42	Study day 49	Study day 56	Every other week to HCT Day 100	HCT Day 100	HCT Day 180	1 Year Post HCT	GVHD Diagnosis or Treatment	Weekly x 4 from start of GVHD Diagnosis or Treatment
Windows	+/- 1 day	Within 2 days of Risk Score Notification	+/- 2 days	+/- 2 days	+/- 2 days	+/- 2 days	+/- 3 days	+/- 3 days	+/- 3 days	+/- 3 days	+/- 6 days	+/- 3 days	+/- 14 days	+/- 14 days	+/- 2 days	+/- 2 days
Eligibility Review	X															
Concomitant Medication Review 	X	X	X	X	X	X	X	X	X	X	X	X	X	X	X	X
Adverse Event Evaluations	X	Adverse events will be reported from the time of the study day 0 through 30 days after the last dose of study drug. Report serious adverse events as they occur.														
Serum Chemistry	X															
GVHD Staging 	X	X	X	X	X	X	X	X	X	X	X	X	X	X	X	X
Alpha-1-antitrypsin Administration		90 mg/kg Once	45 mg/kg Twice weekly for 15 more doses for a total of 16 doses.												If GVHD occurs, continue AAT treatment. Complete 16 doses as per protocol.	
Survival, Relapse & Chronic GVHD Status													X	X	X	
CORRELATIVES STUDIES																
Serum Sample (10 mL) 	X	X	X	X	X	X			X (HCT day 56 +/- 3 days, not study day 56)					X	X	

 When GVHD driven assessments and sample collections occur within 3 days of a calendar based assessment/collection, the calendar assessment/collection is not required.

 Screening occurs on day 7 post-HCT and, if still eligible for screening, again on day 14 post-HCT. Screening samples are sent via overnight shipping to the MAGIC laboratory in New York. Patients who do not meet eligibility by high risk biomarkers will be followed for minimum data collection: GVHD onset date, maximum GVHD severity, steroid refractory GVHD by day 100 (Y/N), chronic GVHD requiring treatment (Y/N), relapse and death with reporting once at one year post-BMT.

 Concomitant medication review will record **only** immunosuppressants and other drugs administered during the reporting period for GVHD prevention and treatment.

 GVHD staging will follow the detailed guidelines provided in the MAGIC Acute GVHD Staging Guidance.

 Serum samples will be banked for correlative studies. To avoid unnecessary sample collection, when GVHD driven samples are collected within 3 days of a scheduled calendar based sample, the calendar based sample should not be collected.

